17.1. INCIDENCE OF AEs (UNIT: %)

Define: an AE is any untoward medical occurrence in the course of a trial, whether or not related to the investigational device.

Evaluation: type, incidence, seriousness and relatedness of AEs/Adverse device effects (ADEs), and laboratory abnormalities will be reported.

Formula: incidence of AEs/ADEs = sum of subject who occurred AEs/ADs ÷sum of subjects for each group×100%.

Statistical method: The incidence of AEs will be summarized by frequency counts along with associated percentages .The Chi square (or Fisher's exact) test will be performed.

17.2. INCIDENCE OF SAEs (UNIT: %)

Define: see relevant subsections of protocol 13.2.1.

Evaluation: incidence, and relatedness of SAEs/Serious adverse device effects (SADEs) will be reported.

Formula: incidence of SAEs/SADEs = sum of subject who occurred SAEs/SADEs ÷sum of subjects for each group×100%.

Statistical method: The incidence of SAEs will be summarized by frequency counts along with associated percentages. The Chi square (or Fisher's exact) test will be performed.

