#### (2) Incidence of SAEs (unit: %)

**Define:** see relevant subsections of Section 12.2.1.

**Evaluation:** incidence, and relatedness of SAEs/Serious adverse device effects (SADEs) will be reported.

**Formula:** incidence of SAEs/SADEs = sum of subject who occurred SAEs/SADEs ÷ sum of subjects for each group × 100%.

**Statistical method:** The difference between investigational group the control group will be assessed.

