## **6.5 Statistical Design, Method and Analytical Procedures**

The descriptive statistics of continuous variables include number, mean, standard deviation, median, minimum and maximum. Frequency and percentage will be used in the descriptive statistics for categorical variables. Unless otherwise specified, all statistical tests will be performed at a significance level of 2.5% (one-sided) with 95% confidence interval (CI).

Detailed statistical methods will be further demonstrated in the statistical analysis plan (SAP).

All statistical analyses will be performed using Statistical Analysis System (SAS) 9.2 version or a later version after database locked according to SAP.

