6.3. SAFETY SET (SS)

Including all subjects who have received either VAC VERAFL0 or control treatment. The data set is used to evaluate the safety of this trial. SS will be analyzed according to the actual treatment group.

7. General Considerations

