7.5. STATISTICAL TESTS

The descriptive statistics of continuous variables include number, mean, standard deviation, median, minimum and maximum. Frequency and percentage will be used in the descriptive statistics for categorical variables. Unless otherwise specified, all statistical tests will be performed at a significance level of 5.0% (two-sided) with two-sided 95% confidence interval (CI).

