17.3. INCIDENCE OF DEVICE DEFICIENCIES RESULTING IN AE OR SAE (UNIT: %)

Define: see relevant subsections of protocol 13.3.1.

Formula: incidence of Device deficiencies resulting in AE or SAE = sum of subjects experienced device deficiency resulting in AE or SAE ÷sum of subjects for each group×100%.

Statistical method: The incidence of Device deficiencies resulting in AE or SAE will be summarized by frequency counts along with associated percentages. The Chi square (or Fisher's exact) test will be performed, P-values will be reported.

18. Safety Outcomes

All outputs for safety outcomes will be based on safety set.

There will be no statistical comparison for safety variables of this study.

Listings will include scheduled, unscheduled, retest and early discontinuation data.

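### SAP 17.1–17.3 compare safety incidences by a test with no estimated difference or interval, SAP 18 says no safety comparison is made, and the test has little power for uncommon harms

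*SAP*

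**What the plan says.** Protocol 4.2 and SAP 3.2 list the comparison of AE, SAE and device-deficiency incidence among the secondary objectives. Protocol 5.3.2 gives the method for each in one general sentence. For SAEs it reads "The difference between investigational group the control group will be assessed".

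The SAP turns this into an analysis in three places, all on the Safety Set:

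- 17.1 (AEs and adverse device effects, ADEs): counts and percentages, then "The Chi square (or Fisher's exact) test will be performed".
- 17.2 (SAEs and serious ADEs, SADEs): "The incidence of SAEs will be summarized by frequency counts along with associated percentages. The Chi square (or Fisher's exact) test will be performed".
- 17.3 (device deficiencies that led to an AE or SAE): counts and percentages, then "The Chi square (or Fisher's exact) test will be performed, P-values will be reported".

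SAP 18, which follows directly, says "There will be no statistical comparison for safety variables of this study".

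The default in SAP 7.5 is "Unless otherwise specified, all statistical tests will be performed at a significance level of 5.0% (two-sided) with two-sided 95% confidence interval (CI"). Protocol 6.5 has a parallel default at one-sided 2.5%, also with a 95% interval. Neither says which quantity the interval estimates for a safety endpoint.

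Elsewhere the SAP does name estimates: a difference of LS means with its 95% CI for wound volume (15.1.3) and wound area (15.2.3), and a hazard ratio for time to completion of wound bed preparation (15.2.2).

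**The concern.** There are two linked problems.

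First, the plan undertakes to assess a difference but never defines an estimate of it. A chi-square or Fisher test asks only whether equal proportions can be rejected. It does not say how large an excess remains compatible with the data, which is what a safety assessment needs. The sample size rests on wound volume alone, so the power of the safety tests is whatever that size happens to give.

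Second, the SAP is inconsistent about whether the comparison happens at all. Under section 17 there is a test without an estimate. Under section 18 there is no comparison, although the objectives call for one. Neither reading gives an estimated difference.

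This is a pre-marketing trial for registration, so the safety tables will be read closely. For uncommon events a non-significant result is likely even if the investigational arm has materially more of them, and the planned output would not show how much is left open.

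**Working it through.** **1. The plan's own sample size.** Inputs from protocol 6.1.1: margin 20%, SD 40%, one-sided 0.025, power 0.80. A true difference of zero is implied but not stated.

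n per arm = 2 × (1.960 + 0.842)² × (0.40/0.20)² = 62.8, so 63 by the normal formula. With the t distribution, 64 per arm gives 80.2% power. The stated 128 evaluable subjects are reproduced.

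Inflated for drop-out: 128/0.90 = 142.2 (stated 140) and 128/0.75 = 170.7 (stated 170). None of these inputs concerns safety.

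**2. Safety denominators.** SAP 6.3 defines the Safety Set as "Including all subjects who have received either VAC VERAFL0 or control treatment. The data set is used to evaluate the safety of this trial". If every randomised subject is treated, that is 70 per arm (140 randomised) to 85 per arm (170 randomised).

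**3. Event rates.** The documents give none. All rates below are assumptions, shown as a range.

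**4. Probability of missing a true excess.** For n per arm and true rates p₁ and p₂:

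power = Σₓ Σᵧ Bin(x; n, p₁) · Bin(y; n, p₂) · 1{p-value(x, y) < 0.05}, and miss rate = 1 − power.

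The level is two-sided 5%, as in SAP 7.5. For the uncorrected chi-square test, the protocol's one-sided 2.5% level in the direction of harm uses the same critical value.

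| Assumed rates | Fisher, 70 / 85 per arm | Uncorrected chi-square, 70 / 85 per arm |
|---|---|---|
| 5% vs 10% | 88.6% / 84.3% | 79.6% / 77.5% |
| 5% vs 15% | 59% / 49% | 48% / 40% |
| 10% vs 20% | 70% / 63% | 62% / 55% |
| 20% vs 30% | 79% / 73% | 72% / 67% |
| 20% vs 35% | 56% / 47% | 48% / 40% |
| 20% vs 40% | 32% / 22% | 25% / 18% |
| 10% vs 30% | 19% / 11% | 14% / 8% |

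For 5% vs 10%:

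- The Yates-corrected chi-square misses 88.6% and 86.3%.
- A rule that uses Fisher only when the smallest expected count is below 5 misses 81.8% and 78.4%. The SAP states no rule for choosing between the tests.
- At 100 per arm, the maximum after sample size re-estimation, the miss rates are still 81.0% (Fisher) and 73.0% (chi-square).

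For rarer events at 85 per arm, 2% vs 4% is missed in 97% (Fisher) or 90% (chi-square).

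**5. Size needed for 80% power at 5% vs 10%.**

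n per arm = [1.960 × √(2 × 0.075 × 0.925) + 0.842 × √(0.05 × 0.95 + 0.10 × 0.90)]² / 0.05² ≈ 435.

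The trial cannot be a powered test of this contrast and need not be. What matters is what it reports.

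**6. What an interval would add.** Illustrative counts: 9/85 investigational against 4/85 control.

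- Difference: 0.1059 − 0.0471 = 0.0588.
- Wilson limits: 0.0567 to 0.1891 and 0.0185 to 0.1148.
- Newcombe lower limit: 0.0588 − √[(0.1059 − 0.0567)² + (0.1148 − 0.0471)²] = −0.025.
- Newcombe upper limit: 0.0588 + √[(0.1891 − 0.1059)² + (0.0471 − 0.0185)²] = 0.147.

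Fisher gives p = 0.25 and the uncorrected chi-square p = 0.15. The test reports no significance, while the interval shows that an excess of up to 14.7 points is not excluded. With identical counts (4/85 in each arm, p = 1.0), the interval is still −7.4 to +7.4 points.

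**The case against.** The strongest reply is that the plan offers more than a bare p-value. Counts and percentages by arm are planned, so the point difference can be read off. SAP 18.1 adds summaries by severity, system organ class, device relation and death. SAP 7.5 and protocol 6.5 attach a 95% interval to statistical tests in general. SAP 8 lets the table templates override the text, and the templates are not among the documents. All of this stands, and it rules out saying that the plan yields only a p-value. But a chi-square or Fisher test has no interval until an effect measure and a method are chosen, and no section chooses them for safety.

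A reader might infer that a non-significant test will be taken as proof of no added harm. The documents do not say so. They set no safety margin and no safety decision rule, and the pass/fail rule in protocol 6.1.5 covers wound volume only. This is a risk of misreading that the plan does not guard against.

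A reader might also infer that the test can never tell a doubling from no excess. That is too strong: 20% vs 40% at 85 per arm is detected in about four trials of five. Nor should the Fisher figures for 5% vs 10% (84–89%) be quoted alone, because the SAP names chi-square first and it misses 78–80%.

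Finally, an interval does not raise power, and low power for rare events is normal in a trial sized on efficacy. That is true. The gain is that the remaining uncertainty becomes visible.

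**Conclusion.** The point holds in this form. SAP 17.1–17.3 plan counts, percentages and a test, with no named risk difference or interval, for incidences whose comparison is a stated objective. SAP 18 contradicts them by ruling out any safety comparison. The generic interval clause does not fill the gap.

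Under an assumed SAE doubling from 5% to 10%, with everyone randomised being treated, the planned test misses the excess in about 78–89% of trials at 70 to 85 per arm, depending on which test is used. The figure depends on the assumed rates: it is higher for rarer events and falls to 18–22% for 20% vs 40% at 85 per arm. For uncommon events, therefore, non-significance would carry little information about excess harm.

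The documents do not support the stronger claim that the sponsor will treat non-significance as evidence of safety. This is a reporting weakness plus an internal contradiction, both cheap to correct before database lock.

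**What to change.** In SAP 17.1–17.3:

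- Make the comparative output the difference in incidence, investigational minus control, with a two-sided 95% CI by a named method (Newcombe or Miettinen-Nurminen), for AEs, ADEs, SAEs, SADEs and device deficiencies.
- Cover all device deficiencies, as protocol 5.3.2 does. SAP 17.3 currently takes only those that led to an AE or SAE.
- State that safety will be interpreted from the interval, including its upper limit.
- Keep any p-value as descriptive, and state that non-significance is not evidence of equal safety.

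In SAP 18, delete or amend the sentence that excludes statistical comparison so that it agrees with section 17. Check that the table templates carry the new column, since SAP 8 gives them priority over the text.

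The cost is SAP wording and one column in the safety tables, with no new data and no change to sample size. The drawback is presentational: the intervals will be wide and look less reassuring than a statement of no significant difference.

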17.3. INCIDENCE OF DEVICE DEFICIENCIES RESULTING IN AE OR SAE (UNIT: %)

Define: see relevant subsections of protocol 13.3.1.

Formula: incidence of Device deficiencies resulting in AE or SAE = sum of subjects experienced device deficiency resulting in AE or SAE ÷sum of subjects for each group×100%.

Statistical method: The incidence of Device deficiencies resulting in AE or SAE will be summarized by frequency counts along with associated percentages. The Chi square (or Fisher's exact) test will be performed, P-values will be reported.

18. Safety Outcomes

All outputs for safety outcomes will be based on safety set.

There will be no statistical comparison for safety variables of this study.

Listings will include scheduled, unscheduled, retest and early discontinuation data.

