##### **4.2 Secondary Objectives**

The secondary objectives are to compare the differences of time to completion of wound bed preparation, wound area reduction rate, wound clinical assessments, incidence of adverse events (AEs) / serious adverse events (SAEs) and device deficiencies in investigational group versus control group.

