### **(3) Incidence of Device Deficiencies (unit: %)**

**Define:** see relevant subsections of Section 12.3.1.

**Formula:** incidence of Device deficiencies = sum of subjects experienced device deficiency ÷ sum of subjects for each group × 100%.

**Statistical method:** The difference between investigational group the control group will be assessed.

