### **12.3 Device Deficiency**

#### **12.3.1 Definition**

Device deficiency refer to any irrational risk in trial, such as tag errors, quality issues, failure, which may threaten subjects' health and safety while investigational device is under normal use.

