This statistical analysis plan (SAP) is based on Protocol KCI.VERAFLO.2018.02., dated 06 September, 2019 (include amended protocol dated 23AUG2022 V2.0).

2. Changes to Planned Analyses as Stated in Protocol

Not applicable.

3. Study Objectives

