18.1.8. DEVICE DEFICIENCY

Device deficiency, device deficiency resulted in an adverse event, and device deficiency resulted in a serious adverse event will be listed separately.

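### SAP 17.3 narrows the protocol's device-deficiency endpoint to deficiencies that led to an AE or SAE, and does not declare the change

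*SAP*

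**What the plan says.** **Protocol.** The secondary objectives (4.2) include a comparison of "device deficiencies in investigational group versus control group", with no condition on outcome. Section 5.3.2(3) gives the formula: "sum of subjects experienced device deficiency ÷ sum of subjects for each group × 100" (per cent). It adds: "The difference between investigational group the control group will be assessed". The definition in 12.3.1 covers "any irrational risk in trial, such as tag errors, quality issues, failure" that may threaten health and safety, so potential harm is enough. Section 6.5.1 requires every safety endpoint to be summarized descriptively by group and overall. Section 6.6 requires analysis methods changed before data lock to be recorded in the SAP.

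**SAP.** Section 3.2 repeats the unqualified objective. Section 17.3 carries the AE/SAE qualifier in its heading, formula and method statement. Its numerator is "sum of subjects experienced device deficiency resulting in AE or SAE", with counts, percentages and a chi-square or Fisher test for that quantity. Section 18.1.8 covers all deficiencies, those that led to an AE and those that led to an SAE, but only as listings: "device deficiency resulted in a serious adverse event will be listed separately". Section 2, headed "Changes to Planned Analyses as Stated in Protocol", is marked as not applicable.

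**The concern.** The two documents attach different numerators to the same secondary objective. A programmer who follows the SAP text would produce a rate for a subset of deficiencies and a listing for the rest. The quantity that the protocol defined, and promised to compare, would not be among the planned summaries.

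This matters because the trial is a pre-marketing registration study of a device, and the control is a different dressing on wall suction. A labelling error or quality fault that harmed nobody is still information about how the device performs. If the any-deficiency rate were worked out only after the listing had been seen, it would be a post hoc calculation of an endpoint that the protocol had specified in advance.

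**Working it through.** Neither document states an expected or observed deficiency rate, so there is no figure to reproduce. The check is a comparison of texts.

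**1. The two formulas.**

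| | Protocol 5.3.2(3) | SAP 17.3 |
|---|---|---|
| Numerator | subjects with any device deficiency | subjects with a device deficiency that led to an AE or SAE |
| Denominator | subjects in each group | subjects in each group (safety set) |
| Comparison | between-group difference assessed | chi-square or Fisher test, on the narrower numerator |

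**2. Is the SAP wording only a clarification?** No. The definition in Protocol 12.3.1 does not require an AE to have occurred. The SAP adds a condition that the protocol does not contain.

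**3. Direction.** Let D be the number of subjects in an arm with any deficiency, A the number with a deficiency that led to an AE or SAE, and N the subjects in the arm. Every subject in A is also in D, so A ≤ D and A/N ≤ D/N. The SAP incidence is therefore equal to or lower than the protocol incidence in each arm. The ratio of the two is A/D, which the documents do not give.

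**4. Illustration (assumed counts).** Take N = 85, the maximum per arm in Protocol 6.1.1, and assume D = 8. The protocol incidence is 8/85 = 9.4%. The SAP incidence depends on A:

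- A = 0: 0/85 = 0%
- A = 1: 1/85 = 1.2%
- A = 8: 8/85 = 9.4%, with no understatement

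The gap therefore runs from nothing to the whole rate. The value D = 8 has no source in the documents.

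**5. Is the protocol quantity planned elsewhere in the SAP?** Sections 3.2 and 4.1 mention deficiencies only as an objective and as data to be collected. Section 18.1.8 is a listing. The adverse-event overview in 18.1.1 has no deficiency row. No SAP section specifies an incidence for deficiencies of any kind.

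**6. Is the change declared?** No. SAP section 2 reports none, although Protocol 6.6 asks for such changes to be recorded there. SAP 3.2 keeps the broader objective, so the planned analysis does not answer the SAP's own stated objective.

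**7. Are the data available?** Yes. The schedule in Protocol 5.5.1 collects device deficiencies at randomization, dressing changes, end of treatment and withdrawal. It has no collection at screening, but no study device is in use then.

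**The case against.** Several points on the other side are fair.

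- **Leaks.** A reader might infer that every harmless device failure drops out of the by-arm results. That is not so: SAP 15.5 summarizes leaks by treatment group whether or not an AE followed. Labelling and quality faults have no equivalent summary.
- **Templates.** A reader might infer that the any-deficiency rate will never be calculated. The documents cannot show that. SAP section 8 gives the output templates priority over the SAP text, and the templates are not available here; one of them may tabulate all deficiencies. The listing in 18.1.8 would also allow the rate to be derived by hand. What can be said is that the SAP text does not specify it.
- **Intent.** A reader might see a deliberate substitution. The documents do not support that. SAP 17.3 cites the definition at protocol 13.3.1, but the current protocol has it at 12.3.1. SAP 4.2 cites the schedule at 7.2.2, but it is now at 5.5.1. Some SAP text may follow a different protocol numbering. The current documents still have to agree.
- **Labelling of the result.** SAP 17.3 states its qualifier openly, so a careful reader would not mistake one rate for the other.
- **Section 18.** This section says that safety variables will not be compared statistically, which contradicts the tests in 17.1 to 17.3. The status of the comparison is therefore unclear for reasons beyond the numerator, and correcting the numerator alone would not settle it.

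These points limit the consequences. They do not remove the mismatch between the two formulas or the missing declaration.

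**Conclusion.** The point holds on the text of the two documents. SAP 17.3 narrows a protocol-defined endpoint that belongs to a secondary objective, and section 2 does not say so. As written, the SAP text plans no rate and no comparison for deficiencies that caused no AE or SAE.

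The size is unknown. It depends on the share of affected subjects whose deficiency led to an AE, and the documents give no basis for estimating that share. It would be too strong to say that the SAP rate must be smaller, because the two are equal if every affected subject had a deficiency that led to an AE or SAE. It would also be too strong to say that the narrowing favours the investigational arm. The restriction applies to both arms, so its effect on the contrast cannot be predicted.

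The endpoint has no hypothesis, margin or alpha attached, and the primary non-inferiority conclusion is unaffected. This is a correction that should be made before database lock. The conclusion assumes that the SAP text governs, which the unseen templates could alter in practice.

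**What to change.** In SAP 17.3, restore the protocol endpoint: subjects with at least one device deficiency of any kind, divided by safety-set subjects, by arm, with the between-arm difference. Keep deficiencies that led to an AE or SAE as a sub-row. If the narrowing is intended, declare and justify it in section 2 instead.

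In the same edit:

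- reconcile the section 18 statement on safety comparisons with the tests in 17.1 to 17.3, so that the status of the restored comparison is clear;
- make the output template match, since it overrides the SAP text;
- correct the cross-reference to the definition, which is at Protocol 12.3.1.

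The cost is a few SAP sentences and one table row. The data are already collected from randomization onward. The small downside for the sponsor is a reported incidence that may be less favourable.

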### 5.3.2 Evaluation of Safety

#### (1) Incidence of AEs (unit: %)

**Define:** an AE is any untoward medical occurrence in the course of a trial, whether or not related to the investigational device.

**Evaluation:** type, incidence, seriousness and relatedness of AEs/Adverse device effects (ADEs), and laboratory abnormalities will be reported.

**Formula:** incidence of AEs/ADEs = sum of subject who occurred AEs/ADs ÷ sum of subjects for each group × 100%.

**Statistical method:** the difference between investigational group and control group will be assessed.

**Note:** especially focus on the systemic reactions and local skin/tissue irritation (such conditions as wound secretions and swelling, pain, and local skin color change, etc.)

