### **Secondary and safety endpoints**

For other continuous secondary endpoints, the same analysis procedure will be conducted as above. In addition, Kaplan-Meier and log rank test will be performed for time to completion of wound bed preparation. An analysis of covariance (ANCOVA) model on mean change in wound area reduction rate as dependent variables with treatment group as fixed factors, site, treatment-by-site interaction (present only if interaction effect is significant) and wound size as covariate will be performed. The difference between the two treatment groups and 95% CI will be reported. The Wilcoxon rank-sum test and Wilcoxon signed rank test will be performed for wound clinical assessments.

In addition, all efficacy and safety endpoints will be summarized descriptively for subjects in each treatment group and overall. The continuous data will be summarized by number of subjects, mean, standard deviation (SD), median, minimum and maximum. The categorical data will be summarized by frequency counts along with associated percentages.

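### SAP section 17 orders between-arm tests on AEs, SAEs and some device deficiencies, section 18 rules out any safety comparison, and the protocol's all-deficiency endpoint is only listed

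*SAP*

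**What the plan says.** **Objective.** Protocol 4.2 includes among the secondary comparisons the "incidence of adverse events (AEs) / serious adverse events (SAEs) and device deficiencies in investigational group versus control group". SAP 3.2 repeats this objective.

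**Protocol method.** For AEs, protocol 5.3.2(1) says "the difference between investigational group and control group will be assessed". For SAEs and for device deficiencies, 5.3.2(2) and (3) say "The difference between investigational group the control group will be assessed". No test is named. In 5.3.2(3) the numerator is every subject with a device deficiency, whatever its consequence. Protocol 6.5.1 adds that "all efficacy and safety endpoints will be summarized descriptively for subjects in each treatment group and overall".

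**SAP section 17.** For AEs (17.1), and in the same words for SAEs (17.2), "The Chi square (or Fisher's exact) test will be performed". SAP 17.3 orders the same test for device deficiencies and adds that p-values are reported: "test will be performed, P-values will be reported". Its numerator is restricted to subjects whose deficiency resulted in an AE or SAE.

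**SAP section 18.** The opening states: "There will be no statistical comparison for safety variables of this study". SAP 18.1.1 then tabulates AEs, SAEs, adverse device effects and serious adverse device effects by treatment group. SAP 18.1.8 provides listings only for device deficiencies.

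**Record of changes.** SAP section 2 declares no changes to the protocol's planned analyses.

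**The concern.** A programmer cannot carry out the tests in section 17 and also obey section 18. Whichever section is followed, the report will depart from the signed SAP in the other.

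Two things are at stake. The first is whether the AE and SAE objective receives any inferential comparison. If section 18 prevails, it does not, and nothing in the SAP marks that as a decision. The second concerns device deficiencies, a natural safety measure for a device trial. The endpoint the protocol defines has neither a test nor a by-arm incidence in the SAP text, whichever section is followed.

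**Working it through.** No figure in the plan bears on this point, so the check is a comparison of the texts, followed by one calculation for scale.

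**Step 1. What each section gives for each protocol safety endpoint.**

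| Protocol 5.3.2 endpoint | Protocol asks | SAP 17 | SAP 18 |
|---|---|---|---|
| AE incidence | difference assessed | chi-square or Fisher | by-arm table, no comparison |
| SAE incidence | difference assessed | chi-square or Fisher | by-arm table, no comparison |
| Device deficiencies, all | difference assessed | not covered | listing only, no comparison |
| Device deficiencies causing an AE or SAE | not a separate endpoint | chi-square or Fisher, p-value | listing only, no comparison |

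The first two rows and the last are in direct conflict between sections 17 and 18. The third row is a gap that exists under either section.

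**Step 2. Can the section 18 sentence be confined to other variables?** It refers to the safety variables of the study as a whole and carries no exception. Section 18.1.1 covers AEs and SAEs, the same variables as 17.1 and 17.2. The wording therefore does not confine it to coded-term (SOC/PT) tables, laboratory data or vital signs, although that may have been the intention.

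**Step 3. Is a change from the protocol recorded?** Protocol 6.6 requires changes to analysis methods made before data lock to be recorded in the SAP. SAP section 2 records none, so neither the absence of a safety comparison nor the narrowing of the deficiency endpoint appears as a change.

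**Step 4. Scale.** How precisely could a difference in incidence be estimated?

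- Per-arm number: 85, the planned maximum of 170 randomised 1:1 (protocol 6.1.1). The safety set counts treated subjects and may be smaller.
- Incidence p, the same in both arms: not given in the documents, so assumed over a range.
- Formula: half-width = 1.96 × √(2p(1 − p)/85).

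| Assumed p | Calculation | Half-width |
|---|---|---|
| 5% | 1.96 × √(0.095/85) | 6.6 points |
| 10% | 1.96 × √(0.18/85) | 9.0 points |
| 20% | 1.96 × √(0.32/85) | 12.0 points |
| 50% | 1.96 × √(0.50/85) | 15.0 points |

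A non-significant p-value could thus sit beside a difference that the data leave quite uncertain, which is the reason to show the interval. The formula is approximate, least so at mid-range incidences and most so at 5%, where only about 4 events per arm are expected (0.05 × 85 = 4.25).

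**The case against.** The strongest reply is that the specific should prevail over the general. SAP 17 mirrors protocol 5.3.2 endpoint by endpoint, while section 18 goes on to coded-term tables, laboratory results, vital signs and examinations. On that reading the tests stand and the section 18 sentence applies to the rest. This is plausible, and the fix below adopts it. But the sentence does not say so, and 18.1.1 repeats AEs and SAEs, so clarification is still needed.

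Other parts of the reply stand in full:

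- A reader might infer that section 18 cancels the comparative safety objective. The documents do not support that for AEs and SAEs. The protocol names no safety test, 6.5.1 promises descriptive summaries, and incidences by arm are tabulated in any case. What is lost is the inferential step.
- A reader might also infer that the sponsor is free to choose after seeing the data. That is not established. SAP section 8 gives the output templates priority over the SAP text, and they may already settle which p-values appear. They are not in the documents.
- SAP 7.5 attaches a two-sided 95% CI to statistical tests by default, so an interval is arguably planned under section 17. However, no safety section names the quantity it would be for.
- A purely descriptive safety plan would be coherent too, if it were stated once and recorded as a change.

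The reply has no answer on device deficiencies. Even the reconciling reading leaves the protocol's all-deficiency endpoint untested and not summarised by arm.

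**Conclusion.** The point holds as an internal inconsistency in the SAP, with a related narrowing of one endpoint. Sections 17 and 18 give incompatible instructions for AE incidence, SAE incidence and deficiencies resulting in an AE or SAE. The protocol's endpoint of all device deficiencies is reduced to a subset in 17.3 and otherwise only listed, with no change recorded.

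The severity is low. No safety hypothesis, power statement or pass/fail rule depends on these tests, and the success criterion rests on the primary endpoint alone. The half-widths of about 7 to 15 points assume 85 treated subjects per arm and equal incidences of 5% to 50%. They describe the precision of a comparison and should not be read as the size of an error caused by the contradiction.

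The conclusion rests on the SAP text. The unseen templates could resolve the conflict in practice, but the text would still need correcting.

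**What to change.** 1. Limit the section 18 sentence to variables not covered by section 17: SOC/PT tables, laboratory data, vital signs and physical examination.
2. In section 17, report the between-group risk difference with its two-sided 95% CI beside the planned test for AEs, SAEs and all device deficiencies as defined in protocol 5.3.2(3). Keep deficiencies resulting in an AE or SAE as an additional row.
3. State that the section 17 p-values are descriptive.
4. Check that the output templates agree, since SAP section 8 gives them priority.

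If the sponsor prefers descriptive safety reporting only, the section 17 tests should be removed and the decision recorded in SAP section 2. The risk differences with intervals would still serve the protocol's stated assessment of the difference.

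The cost is a sentence or two in the SAP and a few table entries. No new data are needed and the primary analysis is unaffected.
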